“Effects of dapagliflozin on blood pressure variability in patients with prediabetes and prehypertension without pharmacological treatment: a randomized”

NCT03006471

June 9, 2016

Introduction

There is a reciprocal relationship between the possibilities of developing arterial hypertension (HT) and diabetes mellitus type 2 (DM2). The probability of developing HT in patients with DM2 is 40% in the first 5 years of diagnosis and 12% in the development of DM2 in HT. The prevention or timely detection of these conditions can reduce the risk of the development of cardiovascular disease (1).

Prediabetes and prehypertension are defined as metabolic states that lead to the appearance of DM2 and HT, respectively.

Approximately 12 million people suffer from prediabetes in Mexico according to the report of the International Diabetes Federation (IDF) in 2017 (2). In 2015, a global prehypertension prevalence of 37.5% will be reported according to the 8th report by the Joint National Committee (JNC8) (3).

Ambulatory blood pressure monitoring (ABPM) is superior to office BP to predict cardiovascular mortality and its most potent component is the alteration in nighttime blood pressure variability (BPV) compared to daytime (4).

Sodium-glucose cotransporter inhibitors type 2 (iSGLT-2) are oral antidiabetics that improve glycemic control. Dapagliflozin promotes natriuresis and osmotic diuresis, which decreases plasma volume and decreases blood pressure (BP) in patients with DM2; however, until now it is unknown whether this effect could modify BPV in individuals with prediabetes and prehypertension without pharmacological treatment (5,6).

Methods

A clinical study, double-blind, randomized and placebo control group in 30 patients. Men and women (30-60 years) diagnosed with prediabetes according criteria of the American Diabetes Association (ADA) with fasting plasma glucose (FPG) 5.6-6.9 mmol/L (>2 occasions) or the 2 h plasma glucose (2-h PG) value during a 75-g oral glucose tolerance test 7.8-11.0 mmol/L, or both (7) and prehypertension according criteria of the JNC8 with BP of 120-139 / 80-89 mmHg (3).

All subjects will be sedentary, non-smokers, without HT, kidney, heart, thyroid or liver disease; pregnant or breastfeeding women will be excluded. They had not consumed any medication during the previous 6 months and all individuals had a stable body weight for at least 3 months prior to the study. Withdrawal of informed consent, loss of follow-up, therapeutic adherence <80% and the presence of serious adverse effects from treatment will be considered criteria for elimination. Dapagliflozin (Forxiga ®Bristol-Myers Squibb, Humacao, Puerto Rico) was given at a dose of 10 mg per day before breakfast for 6 months to 15 patients, while the remaining 15 patients received placebo in the same dose, which will be randomly assigned to one of the intervention groups using a table of numbers. All patients received general nutrition recommendations, as suggested in the ADA guidelines for patients with prediabetes (7), and will be instructed not to modify their usual physical activity.

The enrolled subjects underwent an evaluation at 8:00 a.m. after an overnight fast from 10 to 12 h, will be instructed to avoid strenuous physical activity before clinical and laboratory tests. The body weight and height will be measured with light clothes

and after having evacuated the bladder with digital scale Tanita® TBF-215 A (Corporation of American Inc.)

The body mass index (BMI) will be calculated as body weight (kg) divided by the square of the body height (m²).

Office BP will be assessed after a period of rest with the subject sitting for 15 minutes with a digital sphygmomanometer Omron 907-E (Healthcare, Inc.), the suitable cuff for the circumference of the non-dominant arm will be used (> 80% of the size of the circumference of the cuff) (8). The mean of three measurements of systolic blood pressure (SBP) and diastolic blood pressure (DBP) will be determined.

The FPG and 2-h PG (mmol/l) will be quantified from the serum obtained from a 5 ml sample of venous blood centrifuged at 2500 rpm and the amount of glucose will be determined by colorimetric methods with the automatic clinical chemistry analyzer Erba XL 100™ (Mannheim, Germany), and with an intra- and inter-assay coefficient of variability of < 1% and 2%, respectively. The hemoglobin glycosylated A1c fraction (A1C) (%) will be measured using high-performance liquid chromatography (HPLC) (Bio-Rad Laboratories, Hercules, CA, USA) with an intra- and inter-assay coefficient of variability of 0.4% and 1.6%, respectively.

ABPM will be recorded during 24 h using an oscillometric method with the Microlife WatchBP O3 (Microlife AG, Widnau, Switzerland). BP measurement will be scheduled every 15 minutes during the day (8 a.m. to 11 p.m.) and every 30 minutes during the night (11 p.m. to 8 a.m. of the next day) (8). Patients will be instructed to continue with the usual activities during the ABPM and they will be advised to remain calm when they felt the pressure increase in the cuff. The

method will be considered reliable if more than 70% of valid measurements will be met.

The BPV will be calculated: 24-h BP; daytime and nighttime BP; BP weighted standard deviation (SD) (the average of the daytime and nighttime BP SD each weighted for the duration of the respective day or night period), this method has been proposed as a method of excluding day to night BP changes from the quantification of overall 24 h SD, without discarding either daytime or nighttime values; the coefficient of variation (CV) of 24-h, daytime and nighttime (the average SD of SBP divided by the corresponding mean BP and multiplied by 100); the mean real variability (AVR) of SBP and DBP (the average of the absolute differences between consecutive BP measurements); and identify the dipper circadian BP pattern (BP nightly decline between 10-20% of the BP day, this is normal), Non-dipper (night decrease in BP <20% compared to the BP of the day), dipper reverse (increase in night-time BP compared to day BP), dipper extreme (BP nightly decline between >20% of the BP day) which are relevant to cardiovascular prognosis (9).

Also, will be identified through the ABPM by 24-h: mean arterial pressure (MAP), daytime and nocturnal hypertensive load.

Adherence to treatment and the presence of adverse events will be assessed with an attachment diary that will be given to the patient at study entry, as well as a record of medications and returned by patients at each visit.

The formula for clinical trials will be used to determine the sample size (10), with a statistical confidence of 95% and a power of 80%, as well as the SD and the expected difference for each of the primary variables (11), a total of 8 and 12

patients will be obtained for the SBP and the DBP, respectively. The highest n obtained will be taken into account, to which 20% will be added for possible losses. A total of the 15 patients per group will be estimated in this calculation.

Analysis

Data will be analyzed with the software IBM SPSS Statistics V21.0 software (SPSS, Inc., Chicago, IL, USA)..

The Mann-Whitney U test (non-parametric test for quantitative variables) is used to evaluate the differences between the intervention groups expressed in means and SD; Wilcoxon (non-parametric test for quantitative variables) will be used to evaluate the differences between the baseline and final evaluation of each group expressed in means and SD; and Pearson's Chi2 or Fisher's exact test (non-parametric test for qualitative variables) will be used to evaluate the differences between the intervention groups expressed in frequencies and percentages.

A $p \leq 0.05$ is considered statistically significant.

The present study will be consistent with the Helsinki declaration and will be approved by the Local Committee of Ethics and Research of the University with this register number CEI/357/2016 and Clinical Trials NCT03006471. The informed consent will be obtained from the participants before performing any intervention or evaluation. The principal investigator explained to each participant the nature, risks and benefits of the study.

Financing

The financing will be with own resources by the University of Guadalajara.

References

1. International Diabetes Federation. Atlas de la diabetes de la FID. 2015 [updated in 2015]. Available from: https://www.fundaciondiabetes.org/upload/publicaciones_ficheros/95/IDF_Atlas_2015_SP_WEB_oct2016.pdf.

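### Low adherence and serious adverse effects lead to elimination of randomised patients, and no all-randomised analysis set offsets this

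*Combined protocol and SAP*

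**What the plan says.** The trial is described as "A clinical study, double-blind, randomized and placebo control group in 30 patients", with 15 patients assigned to each arm for 6 months.

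The Methods section gives four reasons for elimination in one sentence. Two are "Withdrawal of informed consent, loss of follow-up". The other two follow directly: "therapeutic adherence <80% and the presence of serious adverse effects from treatment will be considered criteria for elimination". Later in Methods, "Adherence to treatment and the presence of adverse events will be assessed with an attachment diary" and a medication record at each visit, so these last two criteria can be met only once treatment has begun.

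The Analysis section says "The Mann-Whitney U test (non-parametric test for quantitative variables) is used to evaluate the differences between the intervention groups", and that the Wilcoxon test "will be used to evaluate the differences between the baseline and final evaluation of each group". It names the software, the tests and the significance threshold. It does not say which patients enter the tests, how missing final values are handled, or whether eliminated patients are still measured.

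The only related provision is in the sample-size paragraph of Methods: "The highest n obtained will be taken into account, to which 20% will be added for possible losses".

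**The concern.** Randomisation makes the two arms comparable at the start. That protection holds only if patients stay in the comparison for reasons unrelated to treatment and outcome. Here two of the reasons for elimination can be related to both.

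The Introduction attributes natriuresis, osmotic diuresis, lower plasma volume and lower blood pressure to dapagliflozin. It says this of patients with type 2 diabetes, so it is indirect support in a prediabetes trial. Placebo has no such action. Tolerability and adherence can therefore differ by arm and be linked to systolic and diastolic pressure, the primary variables used to size the trial. The wording *from treatment* also calls for a causality judgement, and the plan gives no rule for it.

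If removal is selective, neither the p-value nor the estimated effect is protected by randomisation. In an arm of 15, one patient is 1/15 = 6.7%. There is a safety consequence too: the plan does not say whether adverse events of eliminated patients are counted, so those with the most serious drug-related effects could be absent from the safety report.

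**Working it through.** **The plan's own figure.** The larger base size is 12 (diastolic pressure), read as per group because the final 15 is per group. With a 20% allowance, 12/(1 − 0.20) = 15.0; adding 20% instead gives 12 × 1.20 = 14.4, rounded up to 15. The stated 15 per group reproduces either way. The allowance covers the loss of 3 patients per arm. It protects the number of patients, not the comparability of the arms.

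**Two readings of elimination.** If it means leaving the study, the final values are never collected. If it means only stopping treatment, nothing says the patient is measured at the end and analysed in the assigned arm. Under neither reading are these patients secured in the comparison.

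**Illustration of bias.** Every input below except the 15 per arm and the p ≤ 0.05 threshold is an assumption, because the documents give no removal rates. The model has no true effect and normal outcomes. In each arm the *k* patients highest on a removal score are dropped, and the score has correlation ρ with the outcome.

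The three largest of 15 standard normal values have expectations 1.736, 1.248 and 0.948. Removing *k* patients shifts the mean of those kept by ρ × (sum of the *k* largest)/(15 − *k*):

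- *k* = 1: 1.736/14 = 0.124 × ρ
- *k* = 2: 2.984/13 = 0.230 × ρ
- *k* = 3: 3.932/12 = 0.328 × ρ

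The spurious difference is the shift in one arm minus the shift in the other. For example, 3 v 1 gives (0.328 − 0.124) × ρ = 0.204 × ρ. Type I error comes from simulation: 40,000 trials per cell, exact two-sided Mann-Whitney test, p ≤ 0.05.

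| Removed (active v placebo) | Spurious difference, SD (ρ 0.3 to 1.0) | Type I error, ρ = 0.3 | 0.5 | 0.7 | 1.0 |
|---|---|---|---|---|---|
| 1 v 0 | 0.04 to 0.12 | 4.9% | 5.0% | 5.4% | 6.4% |
| 2 v 1 | 0.03 to 0.11 | 5.2% | 5.3% | 6.1% | 8.3% |
| 2 v 0 | 0.07 to 0.23 | 5.1% | 5.8% | 6.8% | 9.6% |
| 3 v 1 | 0.06 to 0.20 | 5.1% | 5.8% | 7.2% | 11.3% |
| 3 v 0 | 0.10 to 0.33 | 5.4% | 7.0% | 8.7% | 14.1% |
| 3 v 3 | 0 | 4.8% | 5.4% | 6.1% | 8.9% |

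With ρ = 0 there is no spurious difference and type I error is 4.5% to 5.0%. With all 30 analysed it is 4.4%; the exact test is slightly conservative at this size.

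**Power cost of keeping everyone.** The documents do not state the expected difference or SD. Back-solving from 12 per arm and 80% power by the normal approximation gives d = (1.960 + 0.842) × √(2/12) = 1.144 SD. Simulated power of the exact Mann-Whitney test at that effect:

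- 12 v 12, the removed patients left out: about 72%.
- 15 v 15, 3 active patients with no effect: mean effect 12/15 = 80% of its size, power about 60%.
- 15 v 15, 3 active patients with half the effect: mean effect 13.5/15 = 90%, power about 73%.

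**The case against.** The strongest reply is that the plan never says eliminated patients leave the analysis. The word is undefined, and the plan uses the same term, intervention groups, for the groups patients are assigned to and for the groups compared. It is true that exclusion from analysis is an inference, though the natural one given the two neighbouring criteria. The reply does not rescue the plan, because an undefined set leaves the choice open until results are known, and each reading needs the same correction.

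The trial is double-blind, which limits differences between arms in adherence and in judging whether an effect is due to treatment. That stands as mitigation, but blinding cannot equalise tolerability. Nothing in the documents links low adherence to blood pressure directly.

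The upper figures in the table need ρ = 1.0, meaning that the outcome fully determines removal. That is an extreme. At ρ = 0.3 type I error stays between 4.8% and 5.4% across the splits shown, and with a single patient removed it reaches only 6.4% even at the extreme. A material distortion is therefore possible, not demonstrated.

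Finally, retaining patients who gain no benefit can take power to about 60%, below both the 72% with 12 per arm and the 80% target. That cost is real.

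**Conclusion.** The concern holds. The plan states a rule under which randomised patients are eliminated for events that can depend on treatment and outcome, and nothing in it keeps them in the comparison. The between-group result may therefore not compare the groups as randomised.

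The size and direction of any bias cannot be derived from the documents. Under the stated assumptions the effect ranges from none (removal unrelated to outcome) to 0.33 SD and a type I error of 14.1% (3 v 0, ρ = 1.0). Intermediate assumptions give modest inflation, such as 7.0% for 3 v 0 at ρ = 0.5. The case rests on losing the protection of randomisation, not on a predicted bias and not on power. It must be fixed, because it decides who enters the only between-group efficacy comparison and final values that are not collected cannot be recovered. Consent withdrawal and loss to follow-up raise a separate missing-data question, which defining an analysis set does not solve.

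**What to change.** 1. Define elimination, and state that adherence below 80% and adverse effects are not grounds for exclusion from the analysis.
2. Make the primary efficacy analysis all randomised patients in their assigned arm.
3. Carry out the already planned final evaluation in every patient who has not withdrawn consent for follow-up.
4. State a method for final values still missing, for example multiple imputation from baseline value and arm, and say how the results are combined for the planned test. Add a sensitivity analysis suited to a rank test, for example worst rank for missing active patients and best rank for missing placebo patients.
5. Keep adherence of at least 80% as a labelled per-protocol sensitivity analysis.
6. Report adverse events in all patients who took at least one dose, and the number removed or missing by arm and reason.

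This concerns the analysis set and follow-up only, not when study drug is stopped. The direct cost is wording plus final evaluations in a few patients. The estimate would describe the effect of assignment to treatment and may be diluted; the plan should acknowledge the power loss shown above.

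### The non-dipper cut-off (<20%) overlaps almost the whole dipper band (10-20%), so the dipping classes are not mutually exclusive as written

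*Combined protocol and SAP*

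**What the plan says.** In the Methods section, the paragraph on calculating blood pressure variability (BPV) ends with four circadian patterns:

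- Dipper: "dipper circadian BP pattern (BP nightly decline between 10-20% of the BP day, this is normal".
- Non-dipper: "Non-dipper (night decrease in BP <20% compared to the BP of the day".
- Reverse and extreme: "dipper reverse (increase in night-time BP compared to day BP), dipper extreme (BP nightly decline between >20% of the BP day".

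The plan describes these patterns as ones "which are relevant to cardiovascular prognosis (9". It gives no order of precedence among the four rules and does not define them anywhere else. The reference number on that line leads, in the printed list, to an entry whose title concerns the classification and diagnosis of diabetes, so the list as printed does not settle the cut-off.

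The Analysis section does not name dipping pattern. For qualitative variables in general it says "Pearson's Chi2 or Fisher's exact test (non-parametric test for qualitative variables) will be used" to assess "differences between the intervention groups expressed in frequencies and percentages". That this test would be applied to the dipping classes is an inference from the generic sentence.

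**The concern.** A contingency table needs each patient in exactly one cell. Under the written rules a patient with, say, a 15% decline belongs to two classes, one of which the plan calls normal. Two analysts following the text could fill the table differently, and neither could be shown to be wrong. At stake is the reproducibility of one categorical outcome in a trial whose subject is BPV.

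**Working it through.** No figure in the plan depends on these rules, so there is no stated number to reproduce. The check is a logical one, followed by an illustration of size.

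**Inputs.** Let d = 100 × (day BP − night BP) / day BP, the night decline as a percentage of the daytime value. From the Methods section, reading 10-20% as including both ends and "decrease" as d > 0:

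- dipper: 10 ≤ d ≤ 20
- non-dipper: 0 < d < 20
- reverse: d < 0
- extreme: d > 20

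**Step 1: apply the rules as written.**

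| d (%) | Classes met |
|---|---|
| −5 | reverse |
| 0 | none |
| 5 | non-dipper |
| 10 | dipper and non-dipper |
| 15 | dipper and non-dipper |
| 19.9 | dipper and non-dipper |
| 20 | dipper |
| 20.1 | extreme |

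On a grid from −30 to 39.9 in steps of 0.1, all 100 values from 10.0 to 19.9 meet both rules. The only value that is dipper and not non-dipper is 20.0. So if non-dipper were given precedence, the dipper class would hold only patients at exactly 20%.

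**Step 2: find what the other three rules leave free.** Reverse takes d < 0, dipper takes 10 to 20, and extreme takes d > 20. The remainder is 0 ≤ d < 10. With non-dipper set to that range, every value on the same grid falls in exactly one class, with no overlap and no gap.

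**Step 3: size of the overlap (illustration only).** The documents give no distribution of d. Assume it is normal with mean m and standard deviation s. The share in the overlap is

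P(10 ≤ d < 20) = Φ((20 − m)/s) − Φ((10 − m)/s).

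- m = 8, s = 8: Φ(1.5) − Φ(0.25) = 0.334, or 0.334 × 15 = 5.0 patients per arm.
- m = 12, s = 6: Φ(1.333) − Φ(−0.333) = 0.539, or 0.539 × 15 = 8.1 patients per arm.

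These are the extremes over m = 8-12 and s = 6-8, giving 33-54%. Over the wider range m = 5-15 and s = 4-10, the overlap runs from 11% to 79%.

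**Step 4: does the overlap hide a difference between arms?** Take arm means of 8% and 12% with a common s.

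- Literal non-dipper share, P(0 to 20): 0.886, 0.830 and 0.775 at s = 6, 7 and 8, the same in both arms. The difference is 0 because 8 and 12 lie symmetrically about 10.
- Share meeting the dipper rule, P(10 to 20), at s = 6: 0.539 − 0.347 = 0.193 after rounding. At s = 7 and 8 the differences are 0.142 and 0.106. The dipper count as written therefore differs by 10.6 to 19.3 points.
- The near-zero non-dipper difference is not general. With means of 5% and 10% and s = 6, P(0 to 20) is [Φ(2.5) − Φ(−0.833)] = 0.791 against [Φ(1.667) − Φ(−1.667)] = 0.904, a difference of 11.3 points.

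**The case against.** The best defence is that this is a visible slip. The dipper rule starts at 10% and is labelled normal, so a sensible analyst would stop non-dipper at 10%, and nothing would then be distorted. That is a fair reading and largely limits the harm. It does not make the written threshold right: the plan does not state that reading, and the text of record assigns two classes to one patient.

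A reader might infer something stronger: that normal dippers will be reported as non-dippers, or that a treatment effect on dipping will be concealed. The documents do not support either.

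- Both outcomes require non-dipper to override a class the plan calls normal, and nothing in the plan says so. Read literally, a patient at 15% keeps the dipper label as well.
- Even where the literal non-dipper count shows no difference between arms, the count of patients meeting the dipper rule shows one of 10.6 to 19.3 points. The zero itself depends on the means chosen.
- A patient who moves from a 5% to a 15% decline would be non-dipper at both visits under the literal rule, but would also newly meet the dipper rule. The Analysis section states no within-group test for categories: its baseline-to-final test is for quantitative variables.

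The line also does not say whether systolic or diastolic pressure defines the class. That is a separate missing detail and adds no weight here.

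**Conclusion.** Wrong as written, with minor impact. The overlap covers every decline from 10% to just under 20%, and exactly 0% has no class. This follows from the text alone, given only the ordinary reading of "decrease" as a fall and of 10-20% as including its ends. The four classes are neither exclusive nor exhaustive, so a chi-square or Fisher table of dipping pattern is not determined.

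The 33-54% overlap rests wholly on the assumed normal distribution and shows only that the affected band could hold a sizeable share of patients. It is not an estimate of bias. The sample size was set on other variables (the plan says of its totals that "patients will be obtained for the SBP and the DBP, respectively"), and the weighted SD, coefficient of variation and average real variability do not use the classes.

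**What to change.** Replace the non-dipper rule with a night decrease of 0% to <10% of the daytime BP. The set then reads: reverse <0%, non-dipper 0% to <10%, dipper 10-20%, extreme >20%. This brings in no outside threshold, because it is the only range left by the plan's own limits. Apply it to the day and night means from the ambulatory recordings before any unblinded comparison. If the correction is made later, disclose it as such.

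The cost is one line of wording. It needs no new measurement and adds no comparison, and the sample size and continuous measures do not change. If patients have already been classified, their class can be recomputed from the day and night means.

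### The between-arm Mann-Whitney test leaves its scale open, ignores the baseline values collected, and comes with no between-arm difference and confidence interval

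*Combined protocol and SAP*

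**What the plan says.** The Analysis section is the whole statistical plan. For quantitative outcomes it states: "The Mann-Whitney U test (non-parametric test for quantitative variables) is used to evaluate the differences between the intervention groups", with results given as means and SDs. Within each arm, "Wilcoxon (non-parametric test for quantitative variables) will be used to evaluate the differences between the baseline and final evaluation of each group". Categorical outcomes get a chi-squared or Fisher test, and significance is declared at p ≤ 0.05. No covariate, outcome scale, between-arm estimate or CI appears there or elsewhere. The only 95% is the confidence level used for the sample size.

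The sample-size paragraph at the end of Methods uses a formula with 95% confidence and 80% power, "as well as the SD and the expected difference for each of the primary variables", but prints neither figure and does not say whether the SD is that of final values or of changes. It arrives at 8 and 12 "patients will be obtained for the SBP and the DBP, respectively", takes the larger, adds 20% for losses and reaches 15 per group.

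Methods measures both office and ambulatory blood pressure. The ambulatory outcomes include weighted SD, coefficient of variation (CV), average real variability ("the average of the absolute differences between consecutive BP measurements") and "daytime and nocturnal hypertensive load". Entry requires "prehypertension according criteria of the JNC8 with BP of 120-139 / 80-89 mmHg".

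**The concern.** There are three gaps.

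- **Scale.** A Mann-Whitney test on 6-month values and one on changes from baseline are different tests and can disagree. Since the text allows both, the choice could be made after the data are seen.
- **Baseline.** The Wilcoxon tests show that baseline values exist for the same outcomes, yet the between-arm comparison does not use them as a covariate. In a trial of 30 patients this gives up precision that is already paid for.
- **Estimate.** Means and SDs per arm are descriptive. A rank test does not estimate their difference, and no interval is planned. With about 12 analysed per arm, a non-significant p-value without an interval cannot separate no effect from too little information.

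A smaller matter is that the within-arm Wilcoxon tests are not labelled descriptive.

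**Working it through.** **1. The plan's own figure.** 12 × 1.2 = 14.4, rounded up to 15 per group (12/0.8 = 15 gives the same). So 12 is used as a per-group figure. The 8 and 12 cannot be re-derived, because the difference and SD are not printed. Back-solving n per group = 2(z₀.₉₇₅ + z₀.₈₀)²/d²:
- DBP: d = (1.960 + 0.842) × √(2/12) = 1.144 SD
- SBP: d = (1.960 + 0.842) × √(2/8) = 1.401 SD

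**2. Assumptions not in the documents.** Two-sided 5%; normal data; baseline-final correlation r = 0.3/0.5/0.7; k = baseline SD divided by final SD, with k = 1 unless stated; 1.144 read in SDs of the final value. Power comes from simulation (20,000 to 60,000 trials per setting) with the exact Mann-Whitney test, ANCOVA on 2n − 3 degrees of freedom, and rank ANCOVA on joint ranks.

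**3. Variance of each comparison (final value = 1).** Change: 1 + k² − 2rk. ANCOVA: 1 − r². At k = 1 these are 1.40/1.00/0.60 and 0.91/0.75/0.51. Changes beat final values only when r > k/2, so the switch falls at 0.5 only if the two SDs are equal.

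**4. False positives.** On either single scale, Mann-Whitney rejects in 4.3-4.8% of null trials. If the smaller of the two p-values may be reported, the rate is 7.9-8.9% for correlations of 0.3-0.8 at k = 1, and about 7% at k = 0.5. With a true effect at k = 1, the two scales disagree on significance in 17-32% of trials.

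**5. Power at k = 1, r = 0.3/0.5/0.7.**

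| Analysis | 12 per arm | 15 per arm |
|---|---|---|
| Mann-Whitney, final values | 0.73/0.73/0.72 | 0.83/0.83/0.83 |
| Mann-Whitney, changes | 0.58/0.72/0.91 | 0.69/0.83/0.96 |
| ANCOVA | 0.78/0.85/0.95 | 0.87/0.93/0.99 |
| Rank ANCOVA | 0.76/0.82/0.92 | 0.85/0.91/0.97 |

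An unadjusted t-test at 12 per arm has about 0.76, so about 4 points of the shortfall from 0.80 come from the normal-approximation formula, not from omitting baseline. For SBP's 1.40 SD, final-value Mann-Whitney has 0.88 at 12 per arm.

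**6. Smaller baseline SD.** The entry window may narrow the baseline distribution. At r = 0.3/0.5 and 12 per arm, Mann-Whitney on changes has 0.70/0.82 at k = 0.7 and 0.75/0.84 at k = 0.5. ANCOVA (0.78/0.85) and rank ANCOVA (0.76/0.82) do not depend on k. At k = 0.5, ANCOVA leads changes by about 1-4 points and rank ANCOVA is about level with changes.

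**7. If the SD in the sample size is that of change (k = 1).** The effect becomes 1.144 × √(2(1 − r)) final-value SDs. At 12 per arm: final values 0.86/0.73/0.51, changes 0.72-0.73, ANCOVA 0.90/0.86/0.81, rank ANCOVA 0.88/0.82/0.75.

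**8. Skewed outcomes (stress test).** Lognormal data with sigma 0.8, shift of 1.144 raw SD, 12 per arm: final-value Mann-Whitney 0.93, ordinary ANCOVA 0.82/0.86/0.93, rank ANCOVA 0.94/0.97/0.99. With a ratio effect of 1.144 SD on the log scale instead: Mann-Whitney 0.72-0.73, log-scale ANCOVA 0.78/0.85/0.95. Type I error of log-scale ANCOVA is 0.048-0.051.

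**9. Mean 95% CI width, 12 per arm, normal data.** Unadjusted 1.67 SD; adjusted 1.64/1.49/1.23 SD, which is 2%/11%/27% narrower. At r = 0 the adjusted width is 1.72 SD, and 1.72/1.67 = 1.03. Power there is 0.74 for ANCOVA against 0.72 for final-value Mann-Whitney.

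**The case against.** Mann-Whitney is valid under randomisation and is a defensible choice in a small trial. At the planned 15 per arm, final-value Mann-Whitney has 0.83 power under the back-solved effect. At a correlation of 0.3, which the entry window may make plausible for office pressure, ANCOVA adds only 5-6 points at 12 per arm and narrows the CI by 2%. A crude difference can be derived later from the reported means and SDs. The 0.58 for changes depends on equal SDs, which the same entry window makes doubtful.

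The sigma 0.8 lognormal case is also extreme. The variability measures summarise up to 78 scheduled readings (15 h × 4 + 9 h × 2), and nothing in the documents supports such skew. It also borrows DBP's effect size for outcomes that have no stated effect.

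All of this stands, and it limits the size of the gain from adjustment. It does not settle the scale, and a difference worked out afterwards would be unplanned and unadjusted.

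A reader might infer that the between-arm test is wrong, or that the trial is underpowered because it ignores baseline. The documents support neither. The test is valid on one pre-stated scale when all randomised patients are analysed; the elimination criteria in Methods are a separate matter. At 12 per arm and a correlation of 0.3, ANCOVA also falls just short of 80%.

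**Conclusion.** The point holds as a gap in specification and a loss of efficiency. It should be repaired, but it does not invalidate the comparison. The missing scale and the missing estimate with CI are plain omissions and depend on no assumed correlation. The open scale matters most for error control: about 8% false positives instead of about 4.5% if either result could be reported with equal SDs. A reader might take 8% as this trial's error rate. The documents do not say that both scales will be tried, so it is only what the wording permits.

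The benefit of adjustment is less certain in size. It rests on an assumed correlation, SD ratio, normality and a back-solved effect. With equal SDs and 12 per arm, ANCOVA gains about 5-6, 13 and 23 points over final-value Mann-Whitney at correlations of 0.3, 0.5 and 0.7. Over changes, its lead can shrink to 1-4 points if the baseline SD is half the final SD. Nor does ordinary ANCOVA win for every outcome: under strong skew it can fall behind final-value Mann-Whitney, so the adjusted method should depend on the outcome.

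**What to change.** - **SBP and DBP.** Make the primary between-arm analysis ANCOVA of the 6-month value on treatment, with the baseline value of the same measurement as covariate. Apply it to both office and ambulatory pressure and name which is primary. Report the adjusted mean difference with 95% CI, with rank ANCOVA as sensitivity analysis.
- **Weighted SD, CV and average real variability.** Use ANCOVA on the log scale with log baseline as covariate. Report the adjusted ratio of geometric means with 95% CI, with rank ANCOVA as sensitivity analysis.
- **Hypertensive load, which can be zero.** Test with rank ANCOVA and report a baseline-adjusted mean difference with a bootstrap 95% CI. If a Hodges-Lehmann difference is reported instead, state its scale and label it unadjusted.
- **Retained tests.** Fix in advance the scale of any Mann-Whitney test that is kept, and label the within-arm Wilcoxon tests descriptive.

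The cost is SAP wording and one degree of freedom, with no new data or visits. Ordinary ANCOVA assumes linearity and near-normality, hence the rank-based check. If baseline proves unrelated to outcome, the CI is about 3% wider at 12 per arm.
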